3.2 Objectives of the trial

3.2.1 Objective main

The primary objective of the study is to determine whether treatment with everolimus for 24 months prolongs progression-free survival according to RECIST 1.1 criteria. The primary endpoint will be progression-free survival at 24 months in patients receiving hepatic embolization or chemoembolization followed by everolimus therapy.

3.2.2 Secondary objectives

The secondary objectives of the study are to evaluate:

- Progression-free survival at 24 months (hepatic and non-hepatic)
- Overall survival at 24 months
- Tolerance of the treatment during the 24 months of treatment

3.2.3 Exploratory analyses

An exploratory analysis is planned to:

- Search for factors predictive of progression-free survival and/or overall survival
- To compare liver progression-free survival between embolization alone and chemoembolization.

4 Study population

The study includes patients with well-differentiated metastatic NET of the gastrointestinal tract.

4.1 Inclusion criteria

- Histologically proven metastatic endocrine tumor of the gastrointestinal tract (TENPATH review mandatory), well differentiated (grade 1 and 2 according to WHO 2010 classification)
- Predominantly hepatic involvement compared to other metastatic locations requiring embolization or chemoembolization
- Hepatic metastasis(es) measurable according to RECIST V1.1 criteria, unresectable or not accessible to local radiofrequency treatment
- Indication, validated in RCP, for hepatic arterial embolization or chemoembolization for antitumor purposes due to the progressive nature of liver metastases (morphological progression over the last 12 months according to RECIST V1.1 criteria)
- Age \geq 18 years
- General condition WHO \leq 2
- No contraindication to embolization or chemoembolization
- No contraindication to everolimus treatment
- Adequate biological workup:
 - Neutrophils $\geq 1.5 \times 10^9 / L$, platelets $\geq 100 \times 10^9 / L$, Hb $> 10 \text{ g/dL}$
 - Serum bilirubin $\leq 1.5 \times$ upper normal limit (UL), INR < 1.3 (or < 3 on anticoagulants), ALT and AST $\leq 5 \times$ UL
 - Creatinine $\leq 1.5 \times$ LNS
 - 24-hour proteinuria (for patients who will receive streptozotocin for chemoembolization) $< 1.5 \text{ N}$
 - Fasting serum cholesterol $\leq 300 \text{ mg/dL}$ or 7.75 mmol/L and triglycerides $\leq 2.5 \times$ LNS (in the event that one or both of these thresholds are exceeded, the patient can be included in the study only after initiation of appropriate lipid-lowering therapy)
- Complete resolution or persistence with a maximum grade of 1 (except for transaminases or INR if anticoagulant) of toxicities from any previous treatments (NCI CTC version 4.0)
- Minimum time to previous treatment: 28 days
- Information to the patient and signature of an informed consent, after verification of the eligibility criteria
- Affiliation to a social security system

4.2 Non-inclusion criteria

- Duodeno-pancreatic endocrine tumor
- Poorly differentiated and/or grade 3 endocrine tumor
- Indication for embolization or chemoembolization for symptomatic purposes only
- Previous treatment with hepatic arterial embolization or chemoembolization
- Previous treatment with an mTOR inhibitor (somatostatin analogues for anti-secretory purposes are allowed)
- Symptomatic bone metastasis(es)

- Any progressive unbalanced condition: hepatic insufficiency, renal insufficiency, respiratory insufficiency, congestive heart failure NYHA III-IV, unstable angina, myocardial infarction, significant arrhythmias
- Interstitial lung disease
- Patients with uncontrolled diabetes defined as HBa1C > 8
- Patients receiving chronic corticosteroids or immunosuppressants
- Hypersensitivity to everolimus, other rapamycin derivatives or any of the excipients
- Major surgery, open biopsy, or significant traumatic injury within 28 days prior to initiation of study treatment. Incompletely healed wound or anticipated need for major surgery during the course of the study
- Patient with contraindication to vascular occlusion procedures
 - Portal thrombosis
 - Bilio-digestive anastomosis
- HIV patients on antiretroviral therapy
- Malignant pathology within the last 5 years except for basal cell skin carcinoma or cervical cancer *in situ* treated curatively
- Pregnant or breastfeeding woman
- Lack of effective contraception (for men or women of childbearing age)
- Predictable non-compliance
- Medical, geographical, sociological, psychological or legal situation that would prohibit the patient from completing the study or signing an informed consent
- Concurrent patient participation in other experimental research that could influence the primary endpoint of the study

5 Experimental design

5.1 Scheme of the study

This is a single-arm, multi-center Phase II trial.

5.2 Treatment arm

There is a single study treatment arm consisting of:

- 1 to 2 embolization or chemoembolization sessions (sessions spaced 4 to 8 weeks apart).
- 10 mg/day everolimus (started 7 days after embolization or chemoembolization)

[figure not shown]
The maximum treatment period is 24 months.

5.3 Randomization and blinding

The trial is an open-label trial. There is no randomization in this trial.

5.4 Chronological sequence

Each patient will follow the chronological sequence described below:

5.5 Justification of the number of subjects needed

According to the literature, the median progression-free survival after embolization or chemoembolization ranges from 15 to 19 months with a progression-free survival rate of approximately 35% at 24 months. As there is no information on hepatic progression-free survival in the literature, the hypotheses were built on the progression-free survival data.

The assumptions used to calculate the number of subjects are as follows:

- H0: a 24-month progression-free survival rate of less than 35% is not acceptable
- H1: A 24-month liver progression-free survival rate of more than 35% would demonstrate the utility of adjuvant everolimus therapy with an expected 24-month liver progression-free survival rate of 50%,

To obtain a power of 80% with a first-species risk of 5% (one-sided), it is required to include 68 patients according to the assumptions established above (using the exact binomial distribution).

Taking into account a 5% rate of lost to follow-up or patients who cannot be evaluated for any reason except death, **72 patients** will be included.

5.6 Steps of the test

5.6.1 Analysis Final

The final analysis will be performed 24 months after the inclusion of the 72^{ème} patient. The point date for the analysis is therefore: 01/09/2017

Out of 68 evaluable patients, if 31 or more patients are alive without liver progression at 24 months, the treatment will be declared worthwhile.

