5.7.2.2 Survival without liver progression

It is defined as the time from the date of inclusion to the date of first hepatic progression (based on centralized review or on the investigator's opinion in case of impossible review) or the date of death (regardless of cause). Living patients without hepatic progression will be censored at the point date or the date of last morphological evaluation.

Live patients for whom no morphological evaluation is available will be censored at inclusion date + 1 day.

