6.1.2 Population of analysis for primary endpoint (PC)

The analysis population for the primary endpoint is defined as the ITT population of evaluable patients. A patient is considered evaluable if he or she has received at least one dose of everolimus and at least one treatment-related imaging.

A patient who dies (from any cause after treatment) or progresses in liver function before 24 months is evaluable and considered a failure for the primary endpoint.

Patients without a 24-month evaluation will be reviewed according to the following rules:

- If the patient has a later assessment (27 months or more) and is not progressing at that time, then they will be considered progression-free at 24 months
- The other patients will be reviewed at a medical review to decide, in view of the patient's entire file, whether they can be considered as failed or as truly non-evaluable (a rate of 5% of additional patients has been planned for these situations).

A listing of patients excluded from the CP population will be provided with the reasons for their exclusion.

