7.1.7 Statistics

Quantitative variables will be described using the number, median, mean, standard deviation of the mean, minimum, maximum, and interquartile range (Q1-Q3). Quantitative variables may be categorized using their median or a cut-off known from the medical literature.

Categorical variables will be described using percentages, and if necessary their two-sided 95% confidence intervals (calculated using the exact method).

Missing values will not be included in the calculation of frequencies and percentages.

The **confidence intervals** provided will be two-sided 95% confidence intervals, except for the primary criterion where a one-sided 95% confidence interval will be given.

Survival data will be estimated and plotted using the Kaplan-Meier method (Kaplan and Meier, 1958).

This will be described by the median and rates calculated at different times. Two-sided 95% confidence intervals will be provided. Confidence intervals for the rates will be constructed from the Greenwood variance calculated using the log-log transformation.

The median follow-up time will be calculated using the reverse Kaplan-Meier method (Shemper, 1996).

For uni and multivariate analyses, hazard ratios will be estimated using a Cox model (Cox, 1984). The proportionality of the rates will be tested using the graphical representation and the test based on Schöenfeld residuals (Grambsch, 1994); the linearity of the effect of the continuous variables on the risk will be assessed from the graphical representation of the martingale residuals. Confidence intervals for the coefficient estimates of the Cox models will be calculated using the Wald method.

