7.4 Evaluation of the primary endpoint

Population CP

The rate of patients alive without progression at 24 months will be calculated and presented using its one-sided 95% confidence interval (exact confidence interval, binomial distribution).

The results for the primary endpoint will also be described by a Water Fall plot representing for each patient the percentage change at 24 months in liver metastasis size since the measurement at inclusion according to the response according to the RECIST V1.1 criteria.

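### The success rule is stated only for 68 evaluable patients although 72 are enrolled, the criteria for removing a patient from the denominator are not given, and no planned 24-month rate counts removed patients as failures

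*SAP*

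**What the plan says.** SAP 5.5 sets a one-sided 5% exact binomial design, 35% against 50%, needing 68 patients, raised to 72 for a 5% rate of patients lost or not evaluable. SAP 5.6.1 (Analysis Final) then gives the only decision rule in either document: "Out of 68 evaluable patients, if 31 or more patients are alive without liver progression at 24 months, the treatment will be declared worthwhile".

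SAP 6.1.2 (population for the primary endpoint) defines who counts:

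- Basic requirement: "A patient is considered evaluable if he or she has received at least one dose of everolimus and at least one treatment-related imaging".
- Failures: "A patient who dies (from any cause after treatment) or progresses in liver function before 24 months is evaluable and considered a failure".
- A patient with no 24-month evaluation but a progression-free assessment at 27 months or later is a success.
- Everyone else without a 24-month evaluation goes to a medical review of the whole file, which decides "whether they can be considered as failed or as truly non-evaluable (a rate of 5% of additional patients has been planned for these situations"). No criteria are given.
- Transparency: "A listing of patients excluded from the CP population will be provided with the reasons for their exclusion".

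SAP 7.4 analyses the primary rate in this evaluable population only: "The rate of patients alive without progression at 24 months will be calculated and presented using its one-sided 95% confidence interval". SAP 7.1.7 confirms that intervals are two-sided "except for the primary criterion where a one-sided 95% confidence interval will be given". Survival without liver progression is also analysed in the ITT population (SAP 7.5.2), but by Kaplan-Meier, where "Living patients without hepatic progression will be censored at the point date or the date of last morphological evaluation" (SAP 5.7.2.2).

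The protocol synopsis says the analysis is by intention to treat. Protocol XII.3 says efficacy is analysed in evaluable patients.

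**The concern.** In a single-arm trial this one count is the whole efficacy decision, and two of its components are open.

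The first is the cut-off. With 72 enrolled and about 5% expected to drop out, the number evaluable will often not be 68. The design section and the planned interval point to an exact test at whatever number is obtained, but no sentence compares the lower limit with 35% or makes that comparison the decision. At 31 of 70, for example, the stated count is reached while an exact test would need 32, and the SAP does not say which prevails.

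The second is the denominator. The trial is open-label, and the file review has no stated criteria or masking. It can remove patients, and those who never took everolimus leave as well. The wording is also ambiguous for a death or liver progression after embolisation but before everolimus: the dose requirement drops the patient, while the next sentence can be read as counting a failure. No planned analysis of the 24-month rate shows what the removals do to the conclusion, because the ITT Kaplan-Meier analysis censors living patients without progression.

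**Working it through.** **Inputs.** p0 = 0.35, p1 = 0.50, one-sided 5%, exact binomial, 68 needed, 5% loss, 72 enrolled (SAP 5.5); cut-off 31 (SAP 5.6.1). Assumption: loss is independent between patients, so the number evaluable is n ~ Bin(72, 0.95).

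**Step 1. Reproduce the plan.** Type I error = P(X ≥ 31 | 68, 0.35) = 0.0461. Power = P(X ≥ 31 | 68, 0.50) = 0.8019. A cut-off of 30 gives error 0.0752; 32 gives power 0.7277. 68 is the smallest n that reaches 80% power, and 68/0.95 = 71.6, rounded up to 72. The design is right at n = 68.

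**Step 2. Other n.** The matched cut-off is the smallest r with P(X ≥ r | n, 0.35) ≤ 0.05. This is the same as requiring an exact one-sided 95% lower limit above 35%.

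| n | Error with 31 kept | Matched cut-off | Error, matched | Power, matched |
|---|---|---|---|---|
| 65 | 0.0236 | 30 | 0.0414 | 0.7715 |
| 66 | 0.0298 | 31 | 0.0298 | 0.7307 |
| 67 | 0.0373 | 31 | 0.0373 | 0.7681 |
| 68 | 0.0461 | 31 | 0.0461 | 0.8019 |
| 69 | 0.0563 | 32 | 0.0335 | 0.7648 |
| 70 | 0.0680 | 32 | 0.0415 | 0.7985 |
| 71 | 0.0814 | 33 | 0.0302 | 0.7617 |
| 72 | 0.0964 | 33 | 0.0374 | 0.7952 |

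At n = 65, keeping 31 gives power 0.6899 against 0.7715 with 30.

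**Step 3. How often n differs.** P(n > 68) = 0.512, P(66 to 68) = 0.420, P(n < 66) = 0.068, P(n = 72) = 0.025. Averaged over n:

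- 31 kept at every n: error 0.0524, power 0.8085.
- Matched cut-offs: error 0.0378, power 0.7758.

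**Step 4. Removal that depends on outcome.** Let a failure be R times as likely to be removed as a success, with 5% removed overall at p0. The removal probability is s = 0.05/(0.35 + 0.65R) for successes and Rs for failures. The success rate among those kept is 0.35(1 − s)/0.95. With matched cut-offs:

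| R | Share of removals that are failures | Success rate among kept | Type I error |
|---|---|---|---|
| 1 | 0.65 | 0.350 | 0.0378 |
| 2 | 0.79 | 0.357 | 0.0496 |
| 3 | 0.85 | 0.360 | 0.0555 |
| 5 | 0.90 | 0.363 | 0.0614 |
| failures only | 1.00 | 0.368 | 0.0730 |

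**Step 5. The boundary case.** 31/68 has a lower limit of 0.3522, above 35%. If the four other patients are counted as failures, 31/72 has a lower limit of 0.3313 and p = 0.0964.

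**The case against.** The strongest reply is that the rule for other n is already implied. SAP 5.5 fixes an exact one-sided 5% test against 35%, and SAP 7.1.7 and 7.4 present the matching interval. On that reading 31 of 68 merely illustrates the rule at the planned size. Type I error then averages 3.8% with no inflation, and carrying 31 over to 72 ignores the condition in SAP 5.6.1. Even that literal reading averages only 5.2%, and n = 72 has probability of about 2.5%. This stands as a limit on size. It does not supply the missing sentence: the interval is only to be calculated and presented, and the two readings conflict at 69 to 72.

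Second, the review has little room. Deaths after treatment and liver progressions before 24 months are already failures. Scans are read centrally (Protocol X), and CT continues after stopping for a non-hepatic reason (Protocol VIII.2). The review can fail or remove a patient but cannot create a success, and exclusions are listed with reasons. This also stands: inflation needs removals that are heavily failures. But a listing only lets a reader recompute the rate; it does not pre-specify the analysis.

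Third, counting all missing patients as failures cannot separate biased exclusion from ordinary dropout. That is correct, and it is why the analysis should be supportive only.

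Fourth, the synopsis conflict is largely editorial, since SAP 6.1.1 (ITT population) allows exceptions by criterion and SAP 7.4 names the evaluable population. This stands.

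**Conclusion.** The concern holds, as a gap that should be closed rather than an error in the design. At 68 evaluable patients the plan's figures are right. At the planned 5% loss, n exceeds 68 in about half of trials, where the stated count and the implied exact test need different numbers of successes. Reading the count literally costs little on average (5.2% against the nominal 5%) but reaches 9.6% in the worst and unlikely case. With matched cut-offs, outcome-dependent removal takes the error to 5.0% when failures are twice as likely to be removed and to 7.3% when only failures are removed. Only near-boundary results are affected; there, the cut-off chosen or the classification of a few files can decide the declaration. The averages assume independent 5% loss. The removal ratios are illustrative, since the documents give no figure for them.

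**What to change.** Before database freeze, which SAP 7.1.2 allows:

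1. **Decision rule.** Define success as an exact one-sided 95% lower limit above 35% at the actual number evaluable. The cut-offs are 29 for n = 61 to 63, 30 for 64 to 65, 31 for 66 to 68, 32 for 69 to 70 and 33 for 71 to 72.
2. **Sensitivity analysis.** Keep the evaluable population as primary. Beside it, report the 24-month rate with its exact interval on all included patients and on all embolised patients. Count as a failure anyone without documented progression-free status at 24 months or later, with progression as defined in SAP 5.7.1 (Main criterion). Label it supportive, not a second decision rule.
3. **Criteria.** Write down what makes a patient non-evaluable, apply it without knowledge of the success count, and state how a death or liver progression between embolisation and everolimus is counted.
4. **Wording.** Reconcile the synopsis with Protocol XII.3 and SAP 6.1.2.

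**Cost.** No new data, and no change to the primary population or endpoint. Item 1 lowers average power to 77.6%, against 80.9% if 31 were kept throughout. Item 2 gives a lower rate by construction. If 5% of patients become failures independently of outcome, a true 50% becomes 0.50 × 0.95 = 47.5%, and 33/72 is reached with probability about 66%. It would then fall short beside a positive primary result in 12.1% of trials at a true 50% and 2.0% at 35%. The reverse cannot occur, because the matched cut-off never exceeds 33. The all-included version also counts patients whose embolisation was cancelled and who, under Protocol VI.2, do not receive everolimus, so the embolised version belongs beside it.

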5.6.1 Late analysis

Not applicable.

5.7 Judging criteria

5.7.1 Main criterion

The primary endpoint is the rate of living patients without liver progression 24 months after inclusion. Hepatic progression is defined according to RECIST V1.1 criteria and is based on centralized review (or on the investigator's opinion in case of impossible review).

5.7.2 Secondary endpoints of effectiveness

5.7.2.1 Rate of living patients without liver progression in mRECIST at 24 months

The rate of living patients without liver progression 24 months after inclusion will also be described according to mRECIST criteria and based on centralized review.

5.7.2.2 Survival without liver progression

It is defined as the time from the date of inclusion to the date of first hepatic progression (based on centralized review or on the investigator's opinion in case of impossible review) or the date of death (regardless of cause). Living patients without hepatic progression will be censored at the point date or the date of last morphological evaluation.

Live patients for whom no morphological evaluation is available will be censored at inclusion date + 1 day.

5.7.2.3 Progression-free survival

It is defined as the time between the date of inclusion and the date of first hepatic or extrahepatic progression (based on centralized review or on the investigator's opinion in case of unavailable review) or

the date of death (regardless of cause). Patients alive without progression will be censored at the point date or the date of last morphological evaluation.

Live patients for whom no morphological evaluation is available will be censored at inclusion date + 1 day.

5.7.2.4 Overall survival

It is defined as the time between the date of inclusion and the date of death (regardless of cause). Patients lost to follow-up or alive at the time of analysis will be censored at the date of last news.

5.7.3 Secondary tolerability criteria

The following secondary safety endpoints will also be analyzed:

Regarding Embolization/Chimioembolization:

- The number of embolizations and chemoembolizations actually performed per patient;
- The number of embolizations or chemoembolizations planned in PCR;
- The territories of (chemo) embolisations
- Complications during the procedure;
- Post-session complications.

Regarding Everolimus treatment:

- Duration of treatment;
- The time between the end of 1^{ère} (chemo)embolization and the resumption of everolimus therapy;
- The time between the end of 2^{ème} (chemo)embolization and the resumption of everolimus treatment;
- Treatment compliance;
- The number of patients who had at least one dosage change;
- The number of patients who had at least one temporary stop or deferral;
- Toxicities (graded according to NCI-CTC v 4.0).

5.7.1 Other criteria

- The evolution of the WHO performance index
- Best response under treatment (based on centralized review)
- The administration of G-CSF

5.7.2 Exploratory analyses

- An analysis of the predictive factors for overall survival and progression-free survival will be performed;
- In an exploratory manner, the progression-free survival between embolization alone and chemoembolization will be compared (if the number of patients in each group is sufficient).

6 Study population for analysis

6.1 Definition of Analysis Populations

6.1.1 Intent-to-treat (ITT) population

The intention-to-treat population is defined as all patients included in the study, regardless of eligibility criteria and treatment received. All analyses will be performed on an intention-to-treat basis, unless specifically mentioned for certain criteria.

6.1.2 Population of analysis for primary endpoint (PC)

The analysis population for the primary endpoint is defined as the ITT population of evaluable patients. A patient is considered evaluable if he or she has received at least one dose of everolimus and at least one treatment-related imaging.

A patient who dies (from any cause after treatment) or progresses in liver function before 24 months is evaluable and considered a failure for the primary endpoint.

Patients without a 24-month evaluation will be reviewed according to the following rules:

- If the patient has a later assessment (27 months or more) and is not progressing at that time, then they will be considered progression-free at 24 months
- The other patients will be reviewed at a medical review to decide, in view of the patient's entire file, whether they can be considered as failed or as truly non-evaluable (a rate of 5% of additional patients has been planned for these situations).

A listing of patients excluded from the CP population will be provided with the reasons for their exclusion.

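### The primary evaluability rule can never credit a patient lost event-free as a success, so at the SAP's own 5% loss the crude 24-month rate is about 1 point low and the power of the 31/68 rule is about 75-77%, not 80%, if loss is non-informative and spread over follow-up

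*SAP*

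**What the plan says.** SAP 5.5 sizes the trial on true 24-month rates of 35% and 50%: "To obtain a power of 80% with a first-species risk of 5% (one-sided), it is required to include 68 patients", by the exact binomial distribution. It then enrols 72: "Taking into account a 5% rate of lost to follow-up or patients who cannot be evaluated for any reason except death". SAP 5.6.1 gives one decision rule: "Out of 68 evaluable patients, if 31 or more patients are alive without liver progression at 24 months, the treatment will be declared worthwhile". SAP 7.4 analyses a simple proportion in the primary-endpoint population, which "will be calculated and presented using its one-sided 95% confidence interval (exact confidence interval, binomial distribution").

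SAP 6.1.2 (population for the primary endpoint) decides who enters that proportion:

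- At least one everolimus dose and one imaging assessment are required.
- A patient who dies or "progresses in liver function before 24 months is evaluable and considered a failure for the primary endpoint".
- A patient without a 24-month assessment but with a clear scan at 27 months or later counts as progression-free.
- Every other patient without a 24-month assessment goes to a medical review, which classes them as failed or as truly non-evaluable. The 5% extra patients are intended for these cases.

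Hepatic progression-free survival with censoring, estimated by Kaplan-Meier, is a secondary analysis (SAP 5.7.2.2 and 7.5.2).

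**The concern.** Inflating 68 to 72 is sufficient only if the patients removed are a random 5% of those enrolled. Under 6.1.2 they are not. A patient who progresses at month 6 and would have been lost at month 12 stays in as a failure. A patient lost event-free at month 12 who would have been event-free at month 24 leaves the numerator, and at best leaves the denominator too. Exclusion for mid-study loss therefore falls only on patients who have not yet failed, and the remaining proportion estimates something below the 24-month rate used for sizing.

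At stake is the single go/no-go decision of a one-arm trial. If the treatment achieves exactly the planned 50%, the chance of missing success is higher than the 20% the SAP implies. The primary rate would also tend to sit below the trial's own Kaplan-Meier hepatic rate because losses are handled differently.

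**Working it through.** **Inputs.** From SAP 5.5 and 5.6.1: p0 = 0.35, p1 = 0.50, one-sided 5%, 68 evaluable, 72 enrolled, 5% loss, success at 31 or more of 68. Assumed, because the documents do not give them: exponential time to hepatic progression or death, loss independent of prognosis at a constant hazard, and no lost patient returning with a clear scan at 27 months or later.

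**Step 1: the plan's own figures.** P(X ≥ 31 | 68, 0.35) = 0.0461 and P(X ≥ 31 | 68, 0.50) = 0.8019. A cutoff of 30 would give 0.0752, so 31 is correct. 68/0.95 = 71.6, giving 72. The printed figures reproduce when loss causes no bias and exactly 68 are evaluable.

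**Step 2: expected rate under 6.1.2, lost patients excluded.** Let λ = −ln(0.50)/24 = 0.02888 per month be the event hazard and γ the loss hazard.

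- P(success) = 0.50 × exp(−24γ)
- P(lost event-free) = γ/(λ+γ) × [1 − exp(−24(λ+γ))]
- Evaluable rate = P(success) / [1 − P(lost event-free)]

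(a) 5% is the chance of being lost by month 24, with some of those patients having an event first: γ = 0.00214, P(success) = 0.475, P(lost event-free) = 0.0362. Rate = 0.475/0.9638 = 0.493. Mean evaluable n = 72 × 0.9638 = 69.4.

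(b) 5% actually end up lost event-free: γ = 0.00298, P(success) = 0.4655. Rate = 0.4655/0.95 = 0.490. Mean evaluable n = 72 × 0.95 = 68.4.

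The bias is 0.7 to 1.0 percentage point.

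**Step 3: power at a true 50%.**

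| Handling | (a) | (b) |
|---|---|---|
| 31/68 rule, lost patients excluded | 76.7% | 75.3% |
| Averaged over evaluable n out of 72, exact cutoff reset at each n | 74.2% | 72.3% |
| All lost patients classed as failures (n = 72, cutoff 33) | 65.5% | 59.4% |

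Part of the second row is not bias. A random 5% loss with the cutoff reset already gives 77.6%, because 68 is a peak of the exact-binomial sawtooth (76.8% at n = 67, 80.2% at 68, 76.5% at 69). That accounts for about 2.5 points.

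**Step 4: sensitivity to timing, with 5% lost event-free and excluded.**

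| All losses at | Rate | Power, 31/68 | Power, cutoff reset |
|---|---|---|---|
| Inclusion | 0.500 | 80.2% | 77.6% |
| 12 months | 0.489 | 74.8% | 71.8% |
| Just before 24 months | 0.474 | 66.0% | 62.7% |

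**Step 5: type I error.** At a true 35% the expected rate is 0.343 in (a) and 0.339 in (b). Under 31/68 the type I error falls from 4.6% to 3.6% and 3.0%.

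**Step 6: Kaplan-Meier as an alternative.** With exact event times and censoring at loss, simulation of 72 patients gives a mean rate of 0.500, about 80% power and a type I error of 4.2-4.4% for a one-sided 95% log-log lower limit above 35%. Exact event times are unrealistic here. The Protocol (VIII.1) schedules CT every 3 months, ± 1 week, from the first embolization, while SAP 5.7.2.2 starts the clock at inclusion. When events are detected only at scans and the curve is read at 24.0 months from inclusion, progressions found at a late 24-month scan are missed. Simulated type I error rises to about 9% with the ± 1 week window alone. It reaches about 13-14% if a mean delay of about 1.5 weeks from inclusion to embolization is added (assumed); the mean rate is then about 0.39 at a true 0.35. Deaths, which have exact dates, would soften this.

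**The case against.** The strongest reply is that the effect is small and on the safe side. A shift of 0.7 to 1.0 point is about half a patient in 68 (0.01 × 68 = 0.7 at most), against a standard error of √(0.5 × 0.5/68) = 6 points, and no false success is created. This stands and limits the weight of the point. It does not remove the loss of 3.5 to 5 points of power (80.2% to 76.7% or 75.3%).

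Three stronger readings are tempting, and the documents do not support them.

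- A reader might infer that the power is simply 72-74%. SAP 5.6.1 states only 31 of 68, which gives 75-77%. The lower figure needs a cutoff reset at each n, and part of it is discreteness. Keeping 31 as a fixed count whatever the evaluable n would give 80.9% power in (a), but a type I error of 5.2%.
- A reader might infer that the SAP drops everyone lost event-free. It sends them to a review that may also fail them, which costs more power. Some of the 5% may also be non-evaluable from the start: 6.1.2 requires an everolimus dose, and Protocol VI.2 bars everolimus when embolization is cancelled. Such early exclusions cause essentially none of this bias.
- A reader might infer that Kaplan-Meier should become the primary analysis. Read at 24.0 months on this scan schedule, it would exchange a conservative error for an inflated type I error (step 6).

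The downward direction also depends on non-informative loss. If patients leave because they are about to progress, excluding them biases the rate upward, and censoring them in a Kaplan-Meier analysis shares that bias.

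**Conclusion.** The point holds in a limited form. Under 6.1.2 an early event always counts against the treatment, and a patient lost event-free can be saved only by a clear scan at 27 months or later. At the SAP's 5% loss, with non-informative loss spread over follow-up, the power of the stated rule is about 75-77%, and lower if the review classes losses as failures. With such loss and the exact 5% test, the stated 80% holds only if the losses fall near inclusion and exactly 68 patients are evaluable. The documents fix neither the timing of loss nor the review's choice, so any single power figure carries those assumptions. The consequence is a somewhat higher chance of missing a real benefit: roughly 23-25% under 31/68, against the implied 20%.

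**What to change.** Keep the exact binomial rule as the primary analysis.

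1. In SAP 5.5, state that at the planned 5% loss the power of 31/68 is about 75-77%, and 59-66% if all event-free losses are classed as failures. List the assumptions: non-informative loss spread over follow-up and exponential event times.
2. In SAP 7.4, add a named sensitivity analysis beside the primary rate: the Kaplan-Meier hepatic progression-free rate, with event-free losses censored at the last CT and the Greenwood log-log limit already specified in 7.1.7. Read it at the end of the 24-month scan window, or by scheduled visit, and not at 24.0 months from inclusion.

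Both are wording changes that SAP 7.1.2 allows only before the database is frozen. They need no extra patients or data, since the Kaplan-Meier curve is already planned in 7.5.2. The cost is a less favourable stated power and one more sensitivity analysis, which itself assumes non-informative loss.
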